**10.11.6. Safety Figures**

Safety : Figures					
No.	Population	IDSL / TST ID / Example Shell	Title	Programming Notes	Deliverable [Priority]
Cytokine Plots					
2.1	Safety	SAFE_F1	Boxplot of Cytokine Data		SAC [1]
2.2	Safety	SAFE_F2	Individual Cytokine Plot		SAC [1]

## 10.11.7. Pharmacokinetic Tables

Pharmacokinetic : Tables					
No.	Population	IDSL / TST ID / Example Shell	Title	Programming Notes	Deliverable [Priority]
PK Concentration Data					
3.01	PK	PK01	Summary of GSK3342830 Single Dose Plasma Pharmacokinetic Concentration-Time Data (units) by Treatment in Part 1 and Part 3		SAC [1]
3.02	PK	PK01	Summary of GSK3342830 Plasma Pharmacokinetic Concentration-Time Data (units) by Treatment in Part 2		SAC [1]
PK Parameters					
3.03	PK Parameter	PKPT1	Summary of Untransformed GSK3342830 Single Dose Plasma Pharmacokinetic Parameters in Part 1 and Part 3	Tmax, %AUCex, tlast, lambda_z, lambda_z_lower, lambda_z_upper, lambda_z_no. of points	SAC [1]
3.04	PK Parameter	PKPT3	Summary of Log-transformed GSK3342830 Single Dose Plasma Pharmacokinetic Parameters in Part 1 and Part 3	Cmax, AUC(0-t), AUC(0-∞), t1/2, CL, Vss	SAC [1]
3.05	PK Parameter	PKPT1	Summary of Untransformed GSK3342830 Single Dose Urine Pharmacokinetic Parameters in Part 1 and Part 3	Feu(t1-t2), CLr, Ae	SAC [1]
3.06	PK Parameter	PKPT1	Summary of Untransformed GSK3342830 Plasma Pharmacokinetic Parameters in Part 2	Cmax, AUC(0-t), AUC(0-∞), AUC(0-τ), t1/2, CL, Vss, Cτ, Ratio of time invariance, Ratio of accumulation, Tmax, %AUCex, tlast, lambda_z, lambda_z_lower, lambda_z_upper, lambda_z_no. of points	SAC [1]
3.07	PK Parameter	PKPT3	Summary of Log-transformed GSK3342830 Plasma Pharmacokinetic Parameters in Part 2	Cmax, AUC(0-t), AUC(0-∞), AUC(0-τ), t1/2, CL, Vss, Cτ	SAC [1]

Pharmacokinetic : Tables					
No.	Population	IDSL / TST ID / Example Shell	Title	Programming Notes	Deliverable [Priority]
3.08	PK Parameter	PKPT1	Summary of Untransformed GSK3342830 Urine Pharmacokinetic Parameters in Part 2	Feu(t1-t2), CLr, Ae	SAC [1]
PK Analysis Tables					
3.09	PK Parameter	PK_T1	Summary of Statistical Analysis of GSK3342830 Plasma Dose Proportionality in Part 1	C max , AUC(0-∞)	SAC [1]
3.10	PK Parameter	PK_T1	Summary of Statistical Analysis of GSK3342830 Plasma Dose Proportionality in Part 2	C max , AUC(0-τ)	SAC [1]
3.11	PK Parameter	PK_T1	Summary of Statistical Analysis of GSK3342830 Plasma Time Invariance in Part 2	AUC(0-∞) on Day 1 and AUC(0-τ) on Day 15	SAC [1]
3.12	PK Parameter	PK_T1	Summary of Statistical Analysis of GSK3342830 Plasma Accumulation Ratio in Part 2	AUC(0-τ)	SAC [1]
3.13	PK Parameter	PK_T1	Summary of Statistical Analysis of GSK3342830 Plasma Steady State Assessment in Part 2	C τ	SAC [1]
Bayesian Dose Escalation					
3.14	PK Parameter	PK_T2	Summary of Model Parameters for Part 1 - Posterior Distributions		DE [1]
3.15	PK Parameter	PK_T2	Summary of Model Parameters for Part 2 - Posterior Distributions		DE [1]
3.16	PK Parameter	PK_T3	Summary of PK Parameters for Part 1 - Bayesian Prediction of Individual Subjects		DE [1]
3.17	PK Parameter	PK_T3	Summary of PK Parameters for Part 2 - Bayesian Prediction of Individual Subjects		DE [1]
3.18	PK Parameter	PK_T4	Summary of PK Parameters for Part 1 - Bayesian Predictive Probability		DE [1]

Pharmacokinetic : Tables					
No.	Population	IDSL / TST ID / Example Shell	Title	Programming Notes	Deliverable [Priority]
3.19	PK Parameter	PK_T4	Summary of PK Parameters for Part 2 - Bayesian Predictive Probability		DE [1]
3.20	PK Parameter	PK_T4	Summary of PK Parameters for Part 1 - Bayesian Inferential Probability		DE [1]
3.21	PK Parameter	PK_T4	Summary of PK Parameters for Part 2 - Bayesian Inferential Probability		DE [1]
3.22	PK Parameter	PK_T1	Summary of Statistical Analysis of GSK3342830 Single Dose Plasma Pharmacokinetic Parameters in Part 1 and Part 3 Subjects		SAC [1]

## 10.11.8. Pharmacokinetic Figures

Pharmacokinetic : Figures					
No.	Population	IDSL / TST ID / Example Shell	Title	Programming Notes	Deliverable [Priority]
Concentration Plots					
3.01	PK	PKCF4	Mean (SD) GSK3342830 Single Dose Plasma Concentration-Planned Time Plots for Part 1 and Part 3 (Linear and Semi-Log)		SAC [1]
3.02	PK	PKCF5	Median (range) GSK3342830 Single Dose Plasma Concentration-Planned Time Plots for Part 1 and Part 3 (Linear and Semi-Log)		SAC [1]
3.03	PK	PKCF4	Mean (SD) GSK3342830 Plasma Concentration-Planned Time Plots for Part 2 (Linear and Semi-Log)		SAC [1]
3.04	PK	PKCF5	Median (range) GSK3342830 Plasma Concentration-Planned Time Plots for Part 2 (Linear and Semi-Log)		SAC [1]
3.05	PK	PKCF5	Median (range) GSK3342830 Plasma Pre-dose Concentration versus Day for Part 2 (Linear and Semi-Log)		SAC [1]
3.06	PK	PKCF1P	Individual GSK3342830 Single Dose Plasma Concentration-Planned Time Plots for Part 1 and Part 3 (Linear and Semi-Log)		SAC [1]
3.07	PK	PKCF1P	Individual GSK3342830 Plasma Concentration-Planned Time Plots for Part 2 (Linear and Semi-Log)		SAC [1]
PK Parameters					
3.08	PK Parameter	PKPF3	Comparative Plot of Individual GSK3342830 Plasma AUC(0-t) Versus Dose for Part 1		SAC [1]
3.09	PK Parameter	PKPF3	Comparative Plot of Individual GSK3342830 Plasma AUC inf Versus Dose for Part 1		SAC [1]

Pharmacokinetic : Figures					
No.	Population	IDSL / TST ID / Example Shell	Title	Programming Notes	Deliverable [Priority]
3.10	PK Parameter	PKPF3	Comparative Plot of Individual GSK3342830 Plasma Cmax Versus Dose for Part 1		SAC [1]
3.11	PK Parameter	PKPF3	Comparative Plot of Individual GSK3342830 Plasma Ae Versus Dose for Part 1		SAC [1]
3.12	PK Parameter	PKPF3	Comparative Plot of Individual GSK3342830 Plasma AUC(0-t) Versus Dose on Day 1 for Part 2		SAC [1]
3.13	PK Parameter	PKPF3	Comparative Plot of Individual GSK3342830 Plasma AUC(0-∞) Versus Dose on Day 1 for Part 2		SAC [1]
3.14	PK Parameter	PKPF3	Comparative Plot of Individual GSK3342830 Plasma Cmax Versus Dose on Day 1 for Part 2		SAC [1]
3.15	PK Parameter	PKPF3	Comparative Plot of Individual GSK3342830 Plasma Ae Versus Dose on Day 1 for Part 2		SAC [1]
3.16	PK Parameter	PKPF3	Comparative Plot of Individual GSK3342830 Plasma AUCtau Versus Dose on Day 15 for Part 2		SAC [1]
3.17	PK Parameter	PKPF3	Comparative Plot of Individual GSK3342830 Plasma Cmax Versus Dose on Day 15 for Part 2		SAC [1]
3.18	PK Parameter	PKPF3	Comparative Plot of Individual GSK3342830 Plasma Ae Versus Dose on Day 15 for Part 2		SAC [1]
Bayesian Dose Escalation					
3.19	PK Parameter	PK_F1	AUC[0-t] (µg.h/mL) in Part 1 - Dose Response Curve		DE [1]
3.20	PK Parameter	PK_F1	Cmax (µg/mL) in Part 1 - Dose Response Curve		DE [1]
3.21	PK Parameter	PK_F1	AUC[0-24] (µg.h/mL) in Part 2 - Dose Response Curve		DE [1]
3.22	PK Parameter	PK_F1	Cmax (µg/mL) in Part 2 - Dose Response Curve		DE [1]

## 10.11.9. ICH Listings

ICH : Listings					
No.	Population	IDSL / TST ID / Example Shell	Title	Programming Notes	Deliverable [Priority]
Randomisation					
1	Safety	TA1	Listing of Randomized and Actual Treatments		SAC [1]
Subject Disposition					
2	Safety	ES2	Listing of Reasons for Study Withdrawal		SAC [1]
3	Screened	ES7	Listing of Reasons for Screening Failure		SAC [1]
4	Screened	DV2	Listing of Important Protocol Deviations		SAC [1]
5	Safety	IE3	Listing of Subjects with Inclusion/Exclusion Criteria Deviations		SAC [1]
Demographics					
6	Safety	DM2	Listing of Demographic Characteristics	Include height, weight, BMI, Smoking History, Alcohol History, Caffeine History, and Drug Use History	SAC [1]
7	Safety	DM9	Listing of Race		SAC [1]
Medical Conditions and Concomitant Medications					
8	Safety	MH2	Listing of Medical Conditions		SAC [1]
9	Safety	CM3	Listing of Concomitant Medications		SAC [1]
Exposure					
10	Safety	SAFE_L1	Listing of Exposure Data		SAC [1]
Safety					
11	Safety	AE7	Listing of Subject Numbers for Individual Adverse Events		SAC [1]

**CONFIDENTIAL**

204847

ICH : Listings					
No.	Population	IDSL / TST ID / Example Shell	Title	Programming Notes	Deliverable [Priority]
12	Safety	AE8	Listing of All Adverse Events		SAC [1]
13	Safety	AE8	Listing of Drug-Related Adverse Events		SAC [1]
14	Safety	SAFE_L2	Listing of Serious Adverse Events		SAC [1]
15	Safety	AE8	Listing of Adverse Events Leading to Withdrawal from Study		SAC [1]
16	Safety	SAFE_L3	Listing of Infusion Site Reaction Adverse Events	Conditional display	SAC [1]
17	Safety	SAFE_L4	Listing of Liver Adverse Events	Conditional display	SAC [1]
18	Safety	SAFE_L5	Listing of Cardiovascular Adverse Events	Conditional display	SAC [1]
19	Safety	SAFE_L8	Listing of Rash Events	Conditional display	SAC [1]
Laboratory Measurements					
20	Safety	LB5	Listing of Clinical Chemistry Toxicities of Grade 3 or Higher		SAC [1]
21	Safety	LB5	Listing of All Clinical Chemistry Data for Subjects with Toxicities of Grade 3 or Higher		SAC [1]
22	Safety	LB5	Listing of Haematology Toxicities of Grade 3 or Higher		SAC [1]
23	Safety	LB5	Listing of All Haematology Data for Subjects with Toxicities of Grade 3 or Higher		SAC [1]
24	Safety	UR2a	Listing of Urinalysis Toxicities of Grade 3 or Higher		SAC [1]
25	Safety	UR2a	Listing of Urinalysis Data for Subjects with Toxicities of Grade 3 or Higher		SAC [1]
ECGs					
26	Safety	EG5	Listing of Abnormal ECG Findings		SAC [1]
27	Safety	EG5	Listing of All ECG Findings for Subjects with an Abnormal Finding		SAC [1]
28	Safety	EG3	Listing of ECG Values of Potential Clinical Importance		SAC [1]

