5.4.2. Hematological Stopping Criteria

Study treatment will be discontinued for a subject who meets any of the following criteria:

- Hemoglobin ≤ 9.9 g/dL (99 g/L)
- White blood cells $\leq 1999/\text{mm}^3$ ($1.910 \times 10^9/\text{L}$)
- Platelets $\leq 99.999 \times 10^9/\text{L}$

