5.4.3. Renal Stopping Criteria

Study treatment will be discontinued for a subject who meets any of the following criteria:

- Persistent (confirmed on recheck) elevation of serum creatinine (>0.3 mg/dL) without an alternative cause identified
- Albumin to creatinine ratio ≥ 0.03 mg/mg
- New blood in urinalysis confirmed by microscopy without an alternative cause identified

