9.4. Key Elements of Analysis Plan

9.4.1. Primary Analyses

Safety Analyses

The following safety evaluations will be performed:

- Monitoring for AEs
- Routine clinical laboratory tests including chemistry, hematology, and urinalysis
- Vital signs
- Twelve-lead ECG readings
- Continuous cardiac monitoring (dual-lead telemetry)

Safety endpoints will include AEs, clinical laboratory test results (chemistry [including liver function parameters], hematology, and urinalysis), vital signs (BP, heart rate, respiratory rate, and body temperature), and 12-lead ECG readings.

All safety data will be presented in data listings. Subject demographics, medical history, and prior and concomitant medications will be summarized for each dose level using descriptive statistics. For continuous variables, these summaries will include number of subjects, mean, median, standard deviation, minimum, and maximum.

For categorical variables, the summaries will include frequencies and corresponding percentages. No inferential hypothesis testing will be performed on the safety variables.

Adverse events will be coded using the MedDRA classification system.

Treatment-emergent AEs will be defined as any AEs, regardless of relationship to study drug, that occur after the dose of study drug until the Follow-up visit. The treatment-emergent AEs will be summarized for each dose level at AE onset for the overall number of AEs and percentage of subjects who experience them. The total number of AEs will be summarized by dose level and overall. The AEs will be further summarized by severity and relationship to the study drug. If relationship information is missing, the AE will be considered treatment related. Listings for the subsets of SAEs

and treatment-related SAEs will be provided. The SAEs and number of AEs leading to discontinuation will be summarized. The incidence of AEs will also be summarized by system organ class and preferred term.

Clinical laboratory test results, vital signs, and 12-lead ECG results will be summarized by actual values and change from baseline. Clinical laboratory values that are outside of the reference ranges will be flagged and evaluated for clinical significance by the investigator. Any 12-lead ECG abnormalities will be summarized by each dose level. Physical examination findings and cardiac telemetry results will be listed.

Detailed descriptions of the analyses in this study will be presented in the RAP.

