
 
• Reporting for tables, figures and formal statistical analyses :             
 
• Planned time relative to dosing will be used in figures, summaries, statistical analyses and calculation of any derived parameters, unless otherwise stated.
 
• The impact of any major deviation from the planned assessment times and/or scheduled visit days on the analyses and interpretation of the results will be assessed as appropriate.
 
 
 
• Reporting for Data Listings:             
 
• Planned and actual time relative to study drug dosing will be shown in listings (Refer to IDSL Statistical Principle 5.05.1).
 
• Unscheduled or unplanned readings will be presented within the subject's listings.
 
• Visits outside the protocol defined time-windows (i.e. recorded as protocol deviations) will be included in listings but omitted from figures, summaries and statistical analyses.
 
 
 
	
Unscheduled Visits	

 
• Unscheduled visits will not be included in summary tables.
 
• Unscheduled visits will not be included in figures.
 
• All unscheduled visits will be included in listings.
 
	
Descriptive Summary Statistics	
Continuous Data	Refer to IDSL Statistical Principle 6.06.1
Categorical Data	N, n, frequency, %
Reporting of Pharmacokinetic Concentration Data	
Descriptive Summary Statistics	Refer to IDSL Statistical Principle 6.06.1 Assign zero to NQ values (Refer to GUI_51487 for further details)
Reporting of Pharmacokinetic Parameters	
Descriptive Summary Statistics (Log Transformed)	N, n, geometric mean, 95% CI of geometric mean, standard deviation (SD) of logged data and between geometric coefficient of variation (CV b - (%)) will be reported. $CV_b (\%) = \sqrt{(\exp(SD^2) - 1) * 100}$ (SD = SD of log transformed data)

Reporting Standards	
Parameters Not Being Log Transformed	Tmax, %AUCex, tlast, lambda_z, lambda_z_lower, lambda_z_upper, lambda_z_no. of points, Ratio of time invariance, Ratio of accumulation, Feu(t1-t2), CLr, Ae
Listings	Include all following PK parameters: Cmax, AUC0-∞, AUC0-t, AUC(0-τ), t1/2, CL, Vss, Cτ, Ratio of time invariance, Ratio of accumulation, Tmax, %AUCex, tlast, lambda_z, lambda_z_lower, lambda_z_upper, lambda_z_no. of points, Feu(t1-t2), CLr, Ae.
Graphical Displays	

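### SAP Appendix 11 limits the laboratory listings to Grade 3 or higher, above the haematology, creatinine and haematuria stopping limits, so a subject who meets one of those limits may have no laboratory listing

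*SAP*

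**What the plan says.** **Listings.** SAP 10.11.9 plans six listings of routine laboratory values. Listings 20, 22 and 24 show the Grade 3 or higher results for chemistry, haematology ("Listing of Haematology Toxicities of Grade 3 or Higher") and urinalysis. Listings 21, 23 and 25 are the full-data versions, but they cover only subjects who already have such a result: "Listing of All Clinical Chemistry Data for Subjects with Toxicities of Grade 3 or Higher", "Listing of All Haematology Data for Subjects with Toxicities of Grade 3 or Higher" and "Listing of Urinalysis Data for Subjects with Toxicities of Grade 3 or Higher". Listings 32 to 37 concern liver events only.

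**Stopping rules.** Protocol 5.4.2 introduces the hemoglobin, white cell and platelet limits with "Study treatment will be discontinued for a subject who meets any of the following criteria". Protocol 5.4.3 opens the same way. It includes "Persistent (confirmed on recheck) elevation of serum creatinine (>0.3 mg/dL) without an alternative cause identified" and new urinary blood confirmed by microscopy.

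**General commitments.** Protocol 9.4.1 states: "All safety data will be presented in data listings". SAP Table 3 marks an individual listing for chemistry, haematology and urinalysis, with no grade limit, and refers to Appendix 11 for details. SAP 10.5.1 commits to listing all available data from withdrawn subjects. SAP 2.1 declares no change from the protocol's planned analysis.

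**Repeats.** Protocol 5.4 asks for one confirmatory repeat of a laboratory result that meets a stopping criterion. SAP 10.3.3 states: "Unscheduled visits will not be included in summary tables".

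**The concern.** Safety is the primary endpoint and is analysed descriptively, with about 6 to 8 active subjects per cohort. A subject who crosses a protocol stopping limit is among the most informative in the study. A reader of the report will want that subject's baseline, triggering value, confirming repeat and recovery, in order and by dose.

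The SAP generally sets its other listing triggers at or below the matching stopping limit. Vital-sign listings trigger at systolic pressure >160, diastolic >100 and heart rate >110 (SAP 10.6.2), against stops at >160, >100 and >120, each for more than 1 hour (protocol 5.4.5). ECG listings trigger at QTc >450 msec or an increase of at least 60 msec (SAP 10.6.1), against stops at >500 and >60 (protocol 5.4.4). Liver stopping events have their own listings. Haematology and renal stops have no equivalent, although SAP 10.4.3 names hematologic events as being of special interest.

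**Working it through.** The plan gives no figure to reproduce. The check grades each stopping limit with the DMID table in SAP 10.7.1 and asks whether the listing trigger is reached.

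| Criterion | Stopping limit (protocol 5.4.2, 5.4.3) | Grade at the limit | Grade 3 starts at | Stops but triggers no listing |
|---|---|---|---|---|
| Hemoglobin | ≤99 g/L | 1 (95–105) | 79 g/L | 80–99 g/L |
| Platelets | ≤99.999 × 10^9/L | 1 (75–99.999) | below 50 | 50–99.999 |
| White cells (low) | ≤1999/mm³ | none | no low Grade 3; Grade 4 is <1 × 10^9/L | 1.0 up to the limit |
| Creatinine | confirmed rise >0.3 mg/dL | at most 1 | 3.1 × ULN | from the limit to below 3.1 × ULN |
| Haematuria | new, confirmed by microscopy | 1 if microscopic only, <10 RBC/hpf | gross bleeding or red cell casts | anything short of Grade 3 |

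**White cells.** The protocol prints the limit as 1999/mm³ and, in brackets, as 1.910 × 10^9/L. These are not the same number (1999/mm³ = 1.999 × 10^9/L) and should be reconciled. Both are ungraded, because Grades 1 to 3 cover high counts only.

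**Creatinine.** Exclusion criterion 17 bars entry above ULN, so take the baseline as at most ULN. The highest ratio at the limit is then (ULN + 0.3)/ULN. The documents give no ULN, so 0.9 to 1.4 mg/dL is assumed.
- ULN 0.9: (0.9 + 0.3)/0.9 = 1.33 × ULN. Grade 3 needs 3.1 × 0.9 = 2.79 mg/dL.
- ULN 1.4: (1.4 + 0.3)/1.4 = 1.21 × ULN. Grade 3 needs 3.1 × 1.4 = 4.34 mg/dL.

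Both ratios are Grade 1 (1.1 to 1.5 × ULN). Lower baselines give a lower ratio or no grade.

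**ALT.** The stop at ≥3 × ULN coincides with Grade 3 (3.0 to 8.0 × ULN), so it is covered.

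**Confirmatory repeat.** Part 2 laboratory tests are scheduled on Days 2, 5, 10 and 15 and at Follow-up. A prompt repeat is normally unscheduled, so SAP 10.3.3 keeps it out of the summary tables. The same section sends all unscheduled visits to listings, but that has no effect for a subject who triggers no laboratory listing.

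**Where the criteria apply.** Parts 1 and 3 give one infusion, with post-dose laboratory tests on Day 2 and at Follow-up, so no dosing remains to be stopped. Treatment can be stopped on these limits only in Part 2, about 3 × 8 = 24 active subjects. In Parts 1 and 3 the same gap affects a subject who crosses a limit after the single dose. The protocol 4.6.1 risk table lets the renal criteria pause Part 1 progression.

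**The case against.** The strongest reply is that the SAP already commits to these data. SAP 10.5.1 says withdrawn subjects' data will be listed, and protocol 5.4 treats a confirmed laboratory stop as leading to withdrawal. Table 3 marks individual laboratory listings without a grade limit. The gap is then an inconsistency within the SAP, not a decision to hide anyone. That characterisation stands. It does not close the gap: no display in Appendix 11 carries out the 10.5.1 commitment for laboratory values, and Table 3 itself defers to Appendix 11. Nor does 10.5.1 reach a single-dose subject who crosses a limit and completes the study.

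A reader might infer that a stopped subject's values, including recovery, appear nowhere. The documents do not support this. Follow-up is a scheduled visit with chemistry, haematology and urinalysis, and it is a row in the laboratory summary shells. Table 2.7 would show a large scheduled creatinine rise as a maximum change, and Table 2.10 counts occult blood by category and dose.

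A reader might also infer that the report could not show whether the stopping rules were followed. That goes too far. Table 1.2 has a withdrawal reason for reaching a protocol-defined stopping criterion. Listing 2 gives each withdrawn subject's date, study day and reason. Table 1.4 has a deviation category for subjects not withdrawn when they should have been, with important deviations in Listing 4. Listings 12 and 15 may show the adverse event. None of these shells carries the laboratory value.

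Finally, no data are lost. Listings 20 to 25 are final-analysis outputs, not dose-escalation outputs, and missing listings could be produced from the datasets at reporting. This limits the consequence but does not correct the plan as written.

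**Conclusion.** The point holds as an inconsistency between Appendix 11 and protocol 9.4.1, SAP Table 3 and SAP 10.5.1. Five laboratory stopping criteria can be met without reaching the trigger of any laboratory listing. What is then missing is the subject-level laboratory values and the unscheduled confirmatory repeats. Aggregate scheduled values and the record of the withdrawal or event remain.

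It would be too strong to say that every subject stopped on these limits lacks a listing. A subject with a Grade 3 or higher value in the same panel, such as hemoglobin 70 g/L, is listed in full for that panel. May have no listing is the correct wording.

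The conclusion rests on three assumptions. The Grade 3 condition in Listings 21, 23 and 25 is read as applying within each panel. Displays are built from Appendix 11 as written. The creatinine comparison assumes a baseline no higher than ULN and a ULN of 0.9 to 1.4 mg/dL; the margin to 3.1 × ULN is wide across that range. Nothing here questions the stopping limits themselves.

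**What to change.** Either of two changes to SAP Appendix 11 would do:

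1. List all chemistry, haematology and urinalysis data, as protocol 9.4.1 states.
2. Widen the trigger of Listings 20 to 25 to Grade 3 or higher, or any value meeting a protocol Section 5.4 laboratory stopping criterion, and list all scheduled and unscheduled values for those subjects.

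If a restricted trigger is kept, SAP 2.1 should record it as a departure from protocol 9.4.1, and SAP 10.5.1 and Table 3 should be aligned with it.

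The cost is SAP wording, one flag in the laboratory dataset for the second option, and some extra listing pages (few under the second option). No new data are needed.

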**CONFIDENTIAL**

204847

ICH : Listings					
No.	Population	IDSL / TST ID / Example Shell	Title	Programming Notes	Deliverable [Priority]
29	Safety	EG3	Listing of All ECG Values for Subjects with Any Value of Potential Clinical Importance		SAC [1]
Vital Signs					
30	Safety	VS4	Listing of Vital Signs of Potential Clinical Importance		SAC [1]
31	Safety	VS4	Listing of All Vital Signs for Subjects with Potential Clinical Importance Values		SAC [1]
Liver Events					
32	Safety	LIVER5	Listing of Liver Monitoring/Stopping Event Reporting	Conditional display	SAC [1]
33	Safety	MH3	Listing of Medical Conditions for Subjects with Liver Stopping Events	Conditional display	SAC [1]
34	Safety	SAFE_L9	Listing of Alcohol Intake at Onset of Liver Event	Conditional display	SAC [1]
35	Safety	PKCL1X	Listing of Plasma Concentration Data for Subjects with Liver Stopping Events	Conditional display	SAC [1]
36	Safety	LIVER7	Listing of Liver Biopsy Details	Conditional display	SAC [1]
37	Safety	LIVER8	Listing of Liver Imaging Details	Conditional display	SAC [1]
Cardiac Telemetry					
38	Safety	SAFE_L10	Listing of Cardiac Telemetry Monitoring		SAC [1]
39	Safety	SAFE_L11	Listing of Cytokine Data		SAC [1]
Pharmacokinetic Concentration					
40	PK	PKCL1X	Listing of GSK3342830 Pharmacokinetic Plasma Concentration-Time Data by Treatment in Part 1 and Part 3		SAC [1]
41	PK	PKUL1P	Listing of GSK3342830 Pharmacokinetic Urine Concentration-Time Data by Treatment in Part 1 and Part 3		SAC [1]

[figure not shown]

ICH : Listings					
No.	Population	IDSL / TST ID / Example Shell	Title	Programming Notes	Deliverable [Priority]
42	PK	PKCL1X	Listing of GSK3342830 Pharmacokinetic Plasma Concentration-Time Data by Treatment in Part 2		SAC [1]
43	PK	PKUL1P	Listing of GSK3342830 Pharmacokinetic Urine Concentration-Time Data by Treatment in Part 2		SAC [1]
Pharmacokinetic Parameter					
44	PK Parameter	PLPL1X	Listing of GSK3342830 Plasma Pharmacokinetic Parameters by Treatment in Part 1 and Part 3		SAC [1]
45	PK Parameter	PLPL1X	Listing of GSK3342830 Urine Pharmacokinetic Parameters by Treatment in Part 1 and Part 3		SAC [1]
46	PK Parameter	PLPL1X	Listing of GSK3342830 Plasma Pharmacokinetic Parameters by Treatment in Part 2		SAC [1]
47	PK Parameter	PLPL1X	Listing of GSK3342830 Urine Pharmacokinetic Parameters by Treatment in Part 2		SAC [1]

Figure 2.1

Part: xx  
Cytokine Parameter (Unit)

[figure not shown]
Boxplot of Cytokine Data

Programming notes: Present each cytokine parameter on a separate page for all scheduled visits. Include a separate line for each treatment and use different symbols for each treatment. Include a legend to describe the treatments.

Part: xx

Figure 2.2  
Individual Cytokine Plot  
Subject = xxxxx

[figure not shown]
Source Data: Listing 39

Programming notes: Present each subject separately (one per page) and then present all cytokine parameters on the same page for that subject. Include a separate line for each parameter and use different symbols for each parameter. Include a legend to describe the parameters and the units. Present all scheduled results by visit for the x-axis.

[figure not shown]
Figure 3.01  
Mean (SD) GSK3342830 Single Dose Plasma Concentration-Planned Time Plots for Part 1 and Part 3 (Linear and Semi-Log)

Part: Part 1

Linear Scale

Semi-Logarithmic Scale

[figure not shown]

Note to Programmer: Present Part 1 first, then Part 3. Dashed line represents the LLQ. Present all dose levels by part in the same plots. Add legend for doses at the bottom.

[figure not shown]
Figure 3.02  
Median (range) GSK3342830 Single Dose Plasma Concentration-Planned Time Plots  
for Part 1 and Part 3  
(Linear and Semi-Log)

Part: Part 1

Linear Scale

Semi-Logarithmic Scale

[figure not shown]

Note to Programmer: Present Part 1 first, then Part 3. Display dashed line to represent the LLQ. Present all cohort groups in the same plots. Add legend for doses at the bottom.

---

Note: LLQ = xx units  
Source Data: Listing 39

Figure 3.03  
Mean (SD) GSK3342830 Plasma Concentration-Planned Time Plots for Part 2 (Linear and Semi-Log)  
Day: 1

[figure not shown]

Note to Programmer: Display dashed line to represent the LLQ. Present all cohort groups in the same plots. Add legend for doses at the bottom. Repeat for Day 15.

---

Note: LLQ = xx units  
Source Data: Listing 41

Figure 3.04  
Median (range) GSK3342830 Plasma Concentration-Planned Time Plots for Part 2 (Linear and Semi-Log)  
Day : 1

[figure not shown]

Note to Programmer: Display dashed line to represent the LLQ. Present all cohort groups in the same plots. Add legend for doses at the bottom. Repeat for Day 15.

---

Note: LLQ = xx units  
Source Data: Listing 41

Figure 3.05  
Median (range) GSK3342830 Plasma Pre-dose Concentration versus Day for Part 2 (Linear and Semi-Log)

Note to Programmer: Display dashed line to represent the LLQ. Present all cohort groups in the same plots. Add legend for doses at the bottom.

---

Note: LLQ = xx units  
Source Data: Listing 41

[figure not shown]

Example : PKCF1P  
Protocol : 204847  
Population : PK

[figure not shown]
Figure 3.06  
Individual GSK3342830 Single Dose Plasma Concentration-Planned Time Plots for Part 1 and Part 3 (Linear and Semi-Log)  
Subject ID: XXXX

Part: Part 1

Linear Scale

Semi-Logarithmic Scale

Note to Programmer: Present Part 1 first, then Part 3. Display dashed line to represent the LLQ.

---

[figure not shown]
Note: LLQ = xx units  
Source Data: Listing 39

Figure 3.07

[figure not shown]
Individual GSK3342830 Plasma Concentration-Planned Time Plots for Part 2 (Linear and Semi-Log)

Subject ID: XXXX

Linear Scale

Semi-Logarithmic Scale

[figure not shown]

Note to Programmer: Display dashed line to represent the LLQ. Display Day 1 and Day 15 on the same figure.

---

Note: LLQ = xx units  
Source Data: Listing 41

Figure 3.08  
Comparative Plot of Individual GSK3342830 Plasma AUC(0-t) Versus Dose for Part 1 and Part 3

[figure not shown]
---

*Note to Programmer: Present box plot for all cohort groups in the same plot. Place Part 3 at the right end of the axis, footnote will be added for the Part 3 dose.*

Source Data: Listing 43

Figure 3.09

Comparative Plot of Individual GSK3342830 Plasma AUC(0-inf) Versus Dose for Part 1 and Part 3

[figure not shown]
---

*Note to Programmer: Present box plot for all cohort groups in the same plot. Place Part 3 at the right end of the axis, footnote will be added for the Part 3 dose.3*

[figure not shown]
Source Data: Listing 41

Figure 3.10  
Comparative Plot of Individual GSK3342830 Plasma Cmax Versus Dose for Part 1 and Part 3

Linear Scale

Semi-Logarithmic Scale

[figure not shown]
---

*Note to Programmer: Present box plot for all cohort groups in the same plot. Place Part 3 at the right end of the axis, footnote will be added for the Part 3 dose.*

Source Data: Listing 43

Figure 3.11  
Comparative Plot of Individual GSK3342830 Plasma Ae Versus Dose for Part 1

Linear Scale

Semi-Logarithmic Scale

[figure not shown]

---

*Note to Programmer: Present all cohort groups in the same plots.*

Source Data: Listing 44

Figure 3.12  
Comparative Plot of Individual GSK3342830 Plasma AUC(0-t) Versus Dose on Day 1 for Part 2

[figure not shown]

---

*Note to Programmer: Present all cohort groups in the same plots.*

Source Data: Listing 45

Figure 3.13  
Comparative Plot of Individual GSK3342830 Plasma AUC(0-inf) Versus Dose on Day 1 for Part 2

---

[figure not shown]
*Note to Programmer: Present all cohort groups in the same plots.*  
Source Data: Listing 45

[figure not shown]
Figure 3.14

Comparative Plot of Individual GSK3342830 Plasma Cmax Versus Dose on Day 1 for Part 2

Linear Scale

Semi-Logarithmic Scale

[figure not shown]

---

*Note to Programmer: Present all cohort groups in the same plots.*

Source Data: Listing 45

Figure 3.15  
Comparative Plot of Individual GSK3342830 Plasma Ae Versus Dose on Day 1 for Part 2

[figure not shown]
---

*Note to Programmer: Present all cohort groups in the same plots.*  
Source Data: Listing 46

Figure 3.16

Comparative Plot of Individual GSK3342830 Plasma AUC(0-tau) Versus Dose on Day 15 for Part 2

Linear Scale

Semi-Logarithmic Scale

---

[figure not shown]
*Note to Programmer: Present all cohort groups in the same plots.*

Source Data: Listing 45

[figure not shown]
Figure 3.17

Comparative Plot of Individual GSK3342830 Plasma Cmax Versus Dose on Day 15 for Part 2

Linear Scale

Semi-Logarithmic Scale

[figure not shown]

---

*Note to Programmer: Present all cohort groups in the same plots.*

Source Data: Listing 45

[figure not shown]
Figure 3.18  
Comparative Plot of Individual GSK3342830 Plasma Ae Versus Dose on Day 15 for Part 2

---

*Note to Programmer: Present all cohort groups in the same plots.*  
Source Data: Listing 46

Figure 3.19  
AUC(0-t) (µg.h/mL) in Part 1 - Dose Response Curve

Note: The predictive distributions are derived from linear model  $\log\text{-PK-parameter} = \text{intercept} + \text{slope} \cdot \log\text{-dose} + \text{error term}$ .  
Source Table: T3.16

Programming notes:

GlaxoSmithKline

Example : PK\_F1

Protocol : 204847

Population : PK Parameter

Page 1 of n

Figure 3.20

Cmax ( $\mu\text{g/mL}$ ) in Part 1 - Dose Response Curve

Note: The predictive distributions are derived from linear model  $\log\text{-PK-parameter} = \text{intercept} + \text{slope} \cdot \log\text{-dose} + \text{error term}$ .

*Programming notes: repeat figure 3.19 for Cmax ( $\mu\text{g/mL}$ )*

GlaxoSmithKline

Example : PK\_F1

Protocol : 204847

Population : PK Parameter

Page 1 of n

Figure 3.21  
AUC(0-8)x3 ( $\mu\text{g}\cdot\text{h}/\text{mL}$ ) in Part 2 - Dose Response Curve

Note: The predictive distributions are derived from linear model  $\log\text{-PK-parameter} = \text{intercept} + \text{slope}\cdot\log\text{-dose} + \text{error term}$ .  
Source Table: T3.17

*Programming notes: repeat figure 3.19 for AUC[0-8]x3 with X-axis only has 3 dose levels: 1000, 2000, 4000 mg*

GlaxoSmithKline

Example : PK\_F1

Protocol : 204847

Population : PK Parameter

Page 1 of n

Figure 3.22  
Cmax ( $\mu\text{g/mL}$ ) in Part 2 - Dose Response Curve

Note: The predictive distributions are derived from linear model  $\log\text{-PK-parameter} = \text{intercept} + \text{slope} \cdot \log\text{-dose} + \text{error term}$ .  
Source Table: T3.17

*Programming notes: repeat figure 3.19 for Cmax ( $\mu\text{g/mL}$ ) with X-axis only has 3 dose levels: 1000, 2000, 4000 mg*

Example : TA1  
Protocol : 204847  
Population : Randomized

Listing 1  
Listing of Randomized and Actual Treatments

Part: xx

Subject ID.	Cohort	Randomisation Number	Randomization Date	Randomised Treatment	Actual Treatment
xxx	x	xxxxxx	DDMMYYYY	xxxxxxxxxxxxx	xxxxxxxxxxxxx
xxx	x	xxxxxx	DDMMYYYY	xxxxxxxxxxxxx	xxxxxxxxxxxxx

Example : ES2  
Protocol : 204847  
Population : Safety

Listing 2  
Listing of Reasons for Study Withdrawal

Part: xx  
Treatment: xxxx

Subject ID.	Date of Withdrawal	Study Day	Primary Reason
xxx	DDMMYYYY	x	xxxxxxxxxxxxxxxx
xxx	DDMMYYYY	x	xxxxxxxxxxxxxxxx
xxx	DDMMYYYY	x	xxxxxxxxxxxxxxxx
xxx	DDMMYYYY	x	xxxxxxxxxxxxxxxx

Example : ES7  
Protocol : 204847  
Population : Screened

Listing 3  
Listing of Reasons for Screening Failure

Subject ID.	Date of Screen Failure	Reason
xxx	DDMMYYYY	xxxxxxxxxxxxxxxx
xxx	DDMMYYYY	xxxxxxxxxxxxxxxx
xxx	DDMMYYYY	xxxxxxxxxxxxxxxx
xxx	DDMMYYYY	xxxxxxxxxxxxxxxx

Example : DV2  
Protocol : 204847  
Population : Screened

Listing 4  
Listing of Important Protocol Deviations

Part: xx  
Treatment: xxxx

Subject ID.	Date of Deviation/ Study day	Category/ Subcategory	Description	Outcome
xxxxxx/ xxxxxx	ddmmyyyy/ xx	xxxxxxxxxx/ xxxxxxxxxx	xxxxxxxxxxxxxxxxxxxxxxxxxxxx	xxxxxxx
	ddmmyyyy/ xx	xxxxxxxxxx/ xxxxxxxxxx	xxxxxxxxxxxxxxxx	xxxxxxx
xxxxxx/ xxxxxx	ddmmyyyy/ xx	xxxxxxxxxxxxxxxxxxxx	xxxxxxxxxxxxxxxx	xxxxxxx
xxxxxx/ xxxxxx	ddmmyyyy/ xx	xxxxxxxxxx/ xxxxxxxxxx	xxxxxxxxxxxxxxxx	xxxxxxx

Example : IE3  
Protocol : 204847  
Population : Safety

Listing 5  
Listing of Subjects with Inclusion/Exclusion Criteria Deviations

Part: xx  
Treatment: xxxx

Subject ID.	Type	Criterion
xxx	Inclusion	xxxxxxxxxxxxxxxx
xxx	Exclusion	xxxxxxxxxxxxxxxx
xxx	xxxxxxxxxx	xxxxxxxxxxxxxxxx
xxx	xxxxxxxxxx	xxxxxxxxxxxxxxxx

Example : DM2  
Protocol : 204847  
Population : Safety

Listing 6  
Listing of Demographic Characteristics

Part: xx  
Treatment: xxxx

Subject ID.	Year of Birth	Age (yrs)	Sex	Ethnicity	Height (cm)	Weight (kg)	BMI (kg/m  )	History of Smoking/Date Last Smoked	Subject Consume Alcohol/Avg. Consumed Weekly	Subject Consume Caffeine/Avg. Servings per Day	Subjects History of Drug Use
xxxx	YYYY	xx	Female	Hispanic/Latino	xxx.x	xxx.x	xxx.x	Yes	xx	xx	xx
xxxx	YYYY	xx	Female	Not Hispanic/Latino	xxx.x	xxx.x	xxx.x	Yes	xx/DDMMYYYY	xxx/xx	xx

...

Example : DM9  
Protocol : 204847  
Population : Safety

Listing 7  
Listing of Race

Part: xx  
Treatment: xxxx

Subject ID.	Race
xxxx	XXXXXXXXXXXXXXXXXXXXX XXXXXXXXXXXXXXXXXXXXX
xxxx	XXXXXXXXXXXXXXXXXXXXX
...	XXXXXXXXXXXXXXXXXXXXX XXXXXXXXXXXXXXXXXXXXX

GlaxoSmithKline

Example : MH2  
Protocol : 204847  
Population : Randomized

Page 1 of n

Listing 8  
Listing of Medical Conditions

Part: xx  
Treatment: xxxx

Subject	Classification	Condition	Status
PPD - This section has been excluded to protect patient privacy.			

Example : CM3  
Protocol : 204847  
Population : Randomized

Listing 9  
Listing of Concomitant Medications

Part: xx  
Treatment: xxxx

Subj. ID	ATC Level 1/ Ingredient/ Verbatim Text/ Indication	Dose/ Units/ Freq/ Route	Start Date/Time Study Day/ Period Day	Stop Date/Time Study Day/ Period Day	Started Pre- Trial?	Ongoing Medi- cation?
XXXX	Endocrine & metabolic/ Fluticasone propionate/ FLIXOTIDE/ Asthma	2/ MG/ 2XD/ IH	27SEP1999/ 12:30/ 15/ 7			Y

Example : SAFE\_L1  
 Protocol : 204847  
 Population : Safety

Listing 10  
 Listing of Exposure Data

Part: xx  
 Treatment: xxxx

Subject ID.	Treatment	Start Date/Time of Dose	End Date/Time of Dose	Dose Dose Unit	Was infusion interrupted?/ Reason/ Interrupt Date/Time/ Restart Date/Time	Was infusion discontinued?/ Reason/ Discontinuation Date/Time	Did subject receive correct treatment?/ Comment
xxx	XXXXXXX	DDMMYYYY/ hh:mm	DDMMYYYY/ hh:mm	xx xx	No	No	Yes
	XXXXXXX	DDMMYYYY/ hh:mm	DDMMYYYY/ hh:mm	xx xx	Yes/xxxxxxxxxx DDMMYYYY/hh:mm/ DDMMYYYY/hh:mm	Yes/xxxxxxxxxx DDMMYYYY/hh:mm	No/xxxxxxxxxx
	...						

Example : AE7  
Protocol : 204847  
Population : Safety

Listing 11  
Listing of Subject Numbers for Individual Adverse Events

Part: xx  
Treatment: xxxx

System Organ Class

---

Preferred Term	Group	No. with Event	Subject Numbers
SOC #1			
Preferred Term #1	xxxxxx	X	xxxx, xxxxx, xxxxxxxx
